11.2 Run-in treatment start date/time

The run-in treatment start date is the first day of intake of study treatment during the run-in period. It is derived from the first treatment start date (in chronological order) in the **Study Drug Log** eCRF where the 'Study Period' is 'SB RUN-IN'. If the start time of the run-in period is missing, it will be set to 00:00.

11.3 Run-in treatment end date/time

The run-in treatment end date is the last day of intake of run-in study treatment. It is derived from the last DB treatment end date (in chronological order) in the **Study Drug Log** eCRF where the 'Study Period' is 'SB RUN-IN'. If the end time of the run-in period is missing, it will be set to the start time of the DB period minus 1 minute, in the event that the DB period is missing it will be set to 23:59.

11.4 Randomization date/time

The randomization date/time is taken from IVRS.

11.5 Double-blind treatment start date/time

It is the first day of intake of study treatment during the double-blind period. It is derived from the first treatment start date (in chronological order) in the **Study Drug Log** eCRF where the 'Study Period' is 'DB TREATMENT'.

If the date is missing the randomization date (see definition below) is used. If the subject is listed as run-in failure [see definition in Section 5.1] the date is set to ‘missing’. If the start time of the double-blind treatment is missing and the start date of DB period corresponds to the date of Randomization, the Randomization time will be used. In other cases the start time of DB will be set to 00:00.

11.6 Double-blind treatment end date/time

The double-blind treatment end date is the last day of intake of DB study treatment. It is derived from the last DB treatment end date (in chronological order) in the **Study Drug Log** eCRF where the ‘Study Period’ is ‘DB TREATMENT’ and the reason for treatment end is \neq “TEMPORARILY INTERRUPTED DUE TO AN AE” or “TEMPORARILY INTERRUPTED NOT DUE TO AN AE”.

If the study treatment end date is still missing after this derivation, the earliest of the date of Visit 7 - Week 8 / EOT /Part 1 and the date of death (if any) is to be imputed. If the end date is still missing, the EOS date as defined in the Section 2.1 will be used. If the end time of double-blind treatment is missing and DB end date corresponds to the date of the first assessment of ABPM at Visit 7, the time of the first ABPM assessment will be used, otherwise, it will be set to 23:59.

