8.4 Premature End-of-Treatment visit (Visit 9)

All subjects who prematurely discontinue study treatment must have Visit 9 performed as soon as possible but not longer than 7 days after the last dose of study treatment, provided that the subject's consent for this limited participation in the study has not been withdrawn.

Essential hypertension Protocol AC-080A201 Version 3 30 May 2016, page 74/112

Confidential

The following assessments are to be performed at premature EOT / Visit 9:

- Sitting BP and HR, and standing BP, measured by OBPM device.
- Physical examination and body weight.
- *12-lead ECG.
- *Laboratory test (i.e., hematology, blood chemistry, and pregnancy test if applicable).
- *Urinalysis (dipstick by site / UACR by central laboratory).
- Reporting of AEs and SAEs.
- Recording of changes in concomitant medications.
- *Assessment of childbearing potential and recording of changes in contraception methods.
- Check compliance with study treatment.
- Retrieve study treatment bottles.
- Make an appointment for the follow-up telephone call or, *for women of childbearing potential, an appointment for the follow-up visit.
- * If subject discontinued study treatment during run-in period,
- This test may not be performed, and
- For women of childbearing potential, a follow-up telephone call can be made instead of the follow-up visit.

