2 STUDY DESIGN AND FLOW

2.1 Study design

Study AC-080A201 is a prospective, multi-center, double-blind, double-dummy, randomized, placebo- and active-reference, parallel group, Phase 2 dose-finding study with ACT-132577 in subjects with essential hypertension (grade 1 and 2).

Approximately 1000 subjects are enrolled into the study, in order to have at least 540 subjects randomized in the 6 following groups using a 1:1:1:1:1:1 ratio: placebo, 5 mg ACT-132577, 10 mg ACT-132577, 25 mg ACT-132577, 50 mg ACT-132577 and lisinopril 20 mg. At least 420 subjects are expected to complete the trial. There are no stratification factors.

The study consists of the following study periods:

Screening

The screening period starts with the signature of the “study” informed consent form and lasts until Visit 1. During this period study assessments (e.g., laboratory test) are performed to determine whether the subject is eligible for the study.

Run-in period (Period I)

Period I is a single-blind (SB) placebo period of 4 to 6 weeks starting at Visit 1 and ends at Visit 4 / Randomization (after completion of the baseline 24-hour ambulatory blood pressure monitoring [ABPM] recording on the last dose of SB study treatment [placebo]).

The run-in period lasts 4 weeks for anti-hypertensive treatment naïve subjects.

The run-in period lasts 6 weeks for subjects on anti-hypertensive treatment including a 2-week wash-out period for anti-hypertensive treatment. The anti-hypertensive treatment must be discontinued (according to its label) at Visit 1, if there is no contraindication to stop it.

Treatment period (Period II)

Period II is a double-blind (DB) treatment period of 8 weeks which starts at Visit 4 with the first dose of DB study treatment and ends at Visit 7 at the first dose of SB withdrawal treatment.

Withdrawal period (Period III)

Period III is a SB placebo period of 2 weeks, which starts at Visit 7 with the first administration of first placebo dose (withdrawal [WD] study treatment) and ends at Visit 8 (WD-End-of-Treatment [EOT]).

Follow-up period

The follow-up period, including follow-up telephone call, or follow-up visit only for women of childbearing potential to perform the pregnancy test at the site, starts after the last dose of SB WD study treatment (placebo) and ends at 30–33 days after the last dose of the DB treatment.

End-of-Study (EOS)

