End-of-Study (EOS) for a single subject is defined as the date of the follow-up telephone call or follow-up visit.

If a subject withdraws consent and does not wish to participate in the study visits, the date of consent withdrawal is EOS for this subject. If a subject is declared lost to follow-up date of last contact is EOS for this subject.

In addition, unscheduled visits may take place at any time during the study, in which case appropriate assessments may be performed at the discretion of the investigator and must be recorded in the electronic Case Report Form (eCRF).

At the end of the study, the investigator/delegate will explain to the subject what treatment(s) / medical care is necessary and available according to local regulations.

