6 DEFINITION OF PROTOCOL DEVIATIONS

PDs include deviations from inclusion and/or exclusion criteria and deviations from the protocol during the conduct of the study, classified as per latest version of PD code list. Each PD is reported in the SDTM DV domain and categorized according to time period:

1. PD at Screening
2. PD during Run-in period
3. PD at Visit 4 / Pre-randomization

4. PD during DB treatment period
5. PD during withdrawal period and follow-up

Each PD is classified as important or not. Only important PDs during time periods 3, 4 and 5 will be summarized by treatment group for the RND set. (All PDs will be listed.)

Note that an important PD does not necessarily lead to exclusion from the PPS [see Section 7.1.6], whereas an unimportant PD may lead to exclusion from the PPS. The subset of PDs *leading to exclusion* from the PPS are:

1. Double-blind treatment duration less than 49 days: PV_PP.535.
2. No or no valid Week 8 SiDBP (hence, no primary endpoint): PV_PP.501 and PV_MM.501.
3. Anti-hypertensive treatment still ongoing at randomization: PV_MM.307.
4. Taking medication during the double-blind treatment interfering with the primary efficacy parameter (SiDBP): PV_MM.503, PV_MM.504, PV_MM.506, PV_MM.507, PV_MM.508, PV_MM.509, PV_MM.534.
5. Compliance with double-blind treatment < 80% or > 120% or treatment not taken as per protocol: PV_PP.502 and PV_MM.515.

Note that exclusion will be done on a subject basis (rather than on subject / visit basis). In this particular study this approach is not unreasonable since PDs 1–5 are related to the 8 week DB treatment period and the primary efficacy endpoint is measured at the end of that period.

The one PD *leading to exclusion* from the Pharmacokinetic (PK) Set [see Section 7.1.6] is that the PK sample for that subject/visit was not taken at trough: PV_MM.512.

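### When neither the drug log nor Visit 7 supplies a double-blind end date, SAP 11.6 falls back on the End-of-Study date, which adds 30–33 days of exposure for early stoppers who complete follow-up

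*SAP*

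**What the plan says.** SAP 11.6 starts from a clear definition: "The double-blind treatment end date is the last day of intake of DB study treatment". It derives that date in three steps:

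1. The last double-blind record in the study drug log, leaving out records that ended as a temporary interruption.
2. If that yields nothing, the earlier of the Visit 7 Part 1 date and the date of death.
3. Failing both: "If the end date is still missing, the EOS date as defined in the Section 2.1 will be used".

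SAP 2.1 gives EOS three meanings. In the usual case, "End-of-Study (EOS) for a single subject is defined as the date of the follow-up telephone call or follow-up visit", and the follow-up period "ends at 30–33 days after the last dose of the DB treatment". For a subject who withdraws consent it is the withdrawal date, and for a subject lost to follow-up it is the date of last contact.

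Protocol 8.4 provides a visit for early stoppers, who, unless consent is withdrawn, "must have Visit 9 performed as soon as possible but not longer than 7 days after the last dose of study treatment". SAP 11.6 does not mention that visit.

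**The concern.** A subject reaches step 3 only with no usable log date, no Visit 7 and no death. If that subject completes follow-up, the date assigned belongs to a contact deliberately placed about a month after dosing ended. The fallback then contradicts the definition that opens the same section, while a visit tied to within a week of the last dose goes unused.

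A recorded date can also be lost. Protocol 5.1.10 makes a stop of more than 4 consecutive days permanent. If such a stop stays coded in the log as a temporary interruption, step 1 discards its end date.

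The end date feeds several derivations:

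- double-blind duration (SAP 5.3.1), whose table SAP 13.4.1 marks as a key output;
- the compliance denominator (SAP 5.3.2);
- the Per-Protocol Set (PPS) exclusion "Double-blind treatment duration less than 49 days: PV_PP.535";
- the treatment-emergent windows (SAP 5.6), which run to the end date plus 30 days;
- the upper limit of the Week 8 window (SAP 11.1).

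**Working it through.** **The 30–33 days.** The figure agrees with the visit schedule. A completer's last double-blind dose on Day 55 puts the contact at 55 + 30 = Day 85 to 55 + 33 = Day 88. The withdrawal period ends at Day 70, and at least 2 weeks more gives Day 84 or later.

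**Duration.** SAP 5.3.1 uses last dose minus first dose plus 1, so a true last dose on Day s gives s days. With EOS at the follow-up contact, the derived value is s + 30 to s + 33.

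| True last dose | True duration | Derived duration |
|---|---|---|
| Day 14 | 14 | 44–47 |
| Day 28 | 28 | 58–61 |
| Day 40 | 40 | 70–73 |

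At Day 28 the excess is 30/28 = 107% to 33/28 = 118%. The top category in SAP 10.5.1 is more than 8 weeks (56 days). It is reached from Day 27 with a 30-day gap (27 + 30 = 57), or Day 24 with a 33-day gap (24 + 33 = 57).

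**49-day exclusion.** A stop on Day 19 passes with a 30-day gap (19 + 30 = 49), and a stop on Day 16 passes with a 33-day gap (16 + 33 = 49).

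**Compliance.** The denominator is duration × 2 capsules. If every dose was taken and the rest returned, derived compliance is s/(s + 30) to s/(s + 33):

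- Day 19: 19/49 = 39% (30-day gap)
- Day 28: 28/58 = 48.3% to 28/61 = 45.9%
- Day 48: 48/78 = 61.5% to 48/81 = 59.3%

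**Week 8 window.** It runs from Day 43 to the end date. A Visit 9 held within 7 days can reach Day 43 only if the last dose was on Day 36 or later (36 + 7 = 43). For a last dose on Days 36–42, a Visit 9 on Days 43–49 lies after the true end date and outside Week 8. With EOS as the end date, that off-drug reading falls inside Week 8. Later stops before Visit 7 are affected in the same way.

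**Treatment-emergent window.** It closes 30 + 30 = 60 to 33 + 30 = 63 days after the true last dose, instead of 30.

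**Arm mean.** Taking 490/6 ≈ 81.7 subjects per arm (490 is the re-estimated total in SAP 4.2), one affected subject moves mean duration by 30/81.7 = 0.37 to 33/81.7 = 0.40 days. Five would move it by 1.8–2.0 days.

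**The other two EOS meanings.** The error is EOS minus last dose, which the documents do not fix. Assumed gaps of 0, 7 and 14 days turn 28 days into 28, 35 and 42.

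**Using Visit 9.** The error becomes 0–7 days, so a true 28 days is derived as 28–35.

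**The case against.** The strongest reply is that this is a last-resort rule with backstops. Most of it stands.

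- **Rarity.** SAP 12 expects analysis dates to be complete apart from listed types, and this date is not among those types. The log has a code for premature discontinuation (SAP 5.3.3), and data are queried until database closure (Protocol 12.3). The interruption route needs an uncorrected log entry. No affected subject is shown.
- **PPS.** A reader might infer that early stoppers enter the primary analysis because they pass the 49-day rule. The documents mostly do not support this. The same inflated duration lowers compliance to about 39%–62% in the 30-day cases above, and below 80% is itself an exclusion. On-time stoppers up to Day 35 also have no Week 8 value from Visit 9 (35 + 7 = 42). The protection is not complete. Suppose a subject stops on Day 36 and returns none of 144 capsules (four bottles of 36). The true figure is 144/72 = 200%, which is excluded; with a 66-day duration it is 144/132 = 109%, which passes.
- **Adverse events.** A reader might infer a month of extra events. Protocol 10.1.5 and 10.2.2 end routine recording 30 days after actual double-blind discontinuation, so few would be added.
- **Size.** A reader might take 30–33 days as the error for every missing end date. It applies only at step 3, and only when EOS is the follow-up contact.

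None of this removes the exposure error, or the mapping of an off-drug reading to Week 8 in the Full Analysis Set (FAS), which has no duration or compliance screen.

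**Conclusion.** The point holds as a narrow defect in a stated derivation. For an early stopper with no usable log date who completes follow-up, SAP 11.6 returns a date 30–33 days later than the quantity it defines, and it passes over a date at most 7 days late.

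The damage lies mainly in duration and compliance tables. Occasionally it reaches the FAS, where an off-drug Visit 9 reading could count as a Week 8 observation in the mixed model. The effect on the carried-forward analysis is less certain, because the SAP does not say whether such a reading would be carried forward anyway. The documents do not support calling this a material threat to the primary PPS result or to adverse-event counts.

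This rests on three assumptions: the follow-up contact was held on schedule, unused capsules were returned (for the compliance figures), and Visit 9 took place within its 7 days. The number of subjects reaching step 3 is unknown and probably small.

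**What to change.** Reword SAP 11.6 so that, when the present log derivation gives no date, the order is:

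1. The end date of the last double-blind log record, whatever its end reason, provided no later double-blind record exists.
2. Otherwise, the earliest of Visit 7 Part 1, Visit 9 and death.
3. EOS only where it is the consent-withdrawal or last-contact date, never where it is the 30-day follow-up contact.

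Two cautions apply. Do not rank the last intake recorded at a visit above Visit 9. Intake is listed for recording at Visits 5, 6 and 7 but not at Visit 9, so a Day 40 stopper could be given the Day 28 intake from Visit 6 and lose 12 days. Also state that, where the end date is imputed from Visit 9, that visit's blood pressure is not mapped to Week 8. A missing end time defaults to 23:59, so a Day 43–49 reading would otherwise still fall inside the window.

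In the same edit, correct the cross-references in SAP 5.3.1 and 5.6.1.1. They point to 11.2 and 11.4 for the double-blind start and end dates, which are defined in 11.5 and 11.6.

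The cost is a few lines of SAP text and one derivation. The log dates and Visit 9 assessments are already part of data collection.

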11.7 Withdrawal period start date/time

The withdrawal period start date is the first day of intake of placebo during the withdrawal period. It is derived from the first treatment start date (in chronological order) in the **Study Drug Log** eCRF where the ‘Study Period’ is ‘SB WITHDRAWAL’. If the time of the WD period is missing the time of last assessment of ABPM at Visit 7 will be used, otherwise it will be set to 23:59.

11.8 Withdrawal period end date/time

The withdrawal period end date is the date of Visit 8, collected in the **Visit Date** eCRF. If the time is missing it will be set to 23:59.

11.9 Study day

The study day is the number of days elapsed since the day of first DB treatment plus 1 (start of DB treatment is considered Day 1). For dates prior to Day 1, study day is the negative number of days between the date under consideration and the date of first DB treatment. Therefore, the study day is always different from zero.

11.10 Duration of essential hypertension (years)

Duration of essential hypertension (years) = (date of Visit 1 – date of diagnosis)/365.25 with the date of diagnosis collected in the **Essential Hypertension Relevant Disease History** form of the eCRF.

11.11 Unit conversion rules

Height (cm) = height (in) × 2.54

Weight (kg) = weight (lbs) × 0.4536

11.12 Body Mass Index (BMI)

$BMI (kg/m^2) = \text{weight (kg)} / (\text{height [cm]} / 100)^2$

12 HANDLING OF MISSING/INCOMPLETE DATE AND TIME FIELDS

All dates and times used in the analyses are supposed to be complete, apart from the types included in the table below.

The dates in these types that are missing or incomplete are derived as follows:

- 1 Dates are split in 3 parts: year, month and day. Year is the top-level, month is the medium level and day is the low level. If a part expected to contain a number is numeric but the value is outside a valid range, the complete date is handled as missing. For example, if date = 44Nov2000 the whole date is considered to be missing.
- 2 If a part is expected to contain a number is not numeric, i.e., contains values, for example, ND, NA, --, ??, 2?, it is considered as missing.
- 3 If a part is missing, all lower level parts are considered to be missing. This means that a ddmmy date '21ND99' is considered as '----99'.
- 4 Missing parts are changed into acceptable non-missing values in a way depending on the type of date to be replaced.

In the following, 'lower limit' and 'upper limit' refer to the minimum or maximum, respectively, of a possible date. For example, if the day is missing, the lowest limit is the first day of the given month and the upper limit is the last day of the given month. If the day and month are missing, the lower limit refers to the first day of the given year and the upper limit to the last day of the given year. The earliest and the latest of different dates refer to the first or last date, respectively, when ordered in sequence.

Type of date	Date is incomplete	Date is missing
AE resolution date	The upper limit.	No replacement, the AE is considered as ongoing in the analysis.

Type of date	Date is incomplete	Date is missing
AE onset date	If the end date of the AE is not before the start of double-blind treatment, and if the study treatment start falls in the range of possible dates, the study treatment start date is used. In all the other cases the lower limit is used.	Whichever is the earlier of the date of resolution of the AE and the study treatment start date.
Medical history end date	The upper limit.	No replacement.
Medical history start date	The lower limit.	No replacement.
Concomitant medication end date	If the answer to the question ‘Ongoing at start of treatment?’ in the Previous/Concomitant Medication eCRF is answered ‘No’ or if the study treatment start date-1 falls in the range of possible dates, the study treatment start date-1 is used. In all the other cases the upper limit is used.	No replacement. If the answer to the question ‘Ongoing at start of treatment?’ in the Previous/Concomitant Medication eCRF is answered ‘Yes’ the therapy is considered to have finished after the start of treatment.
Concomitant medication start date	
If the end date of the medication is not before the informed consent signature date and if the informed consent date falls in the range of possible dates, the informed consent date is used.
 
If the end date of the medication is not before the study treatment start date and if the study treatment start date falls in the range of possible dates, the study treatment start date is used.
 
In all the other cases the lower limit is used.
	No replacement. The medication is considered to have started before the date of consent.

Type of date	Date is incomplete	Date is missing
Hospitalization discharge date	The upper limit is used.	No replacement. The hospitalization is considered as ongoing in the analysis.
Hospitalization admission date	If the onset date of the AE leading to hospitalization falls in the range of possible dates, the onset date of the AE is used. In all the other cases the lower limit is used.	The onset date of the AE leading to hospitalization is used.

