5.6.1.1 Treatment-emergent adverse events

Double-blind treatment-emergent AEs are defined as those AEs with onset on or after the double-blind treatment start date [see definition in Section 11.2] up to the double-blind treatment end date [see definition in Section 11.4] plus 30 days (included). Run-in treatment-emergent AEs are AEs with onset dates between the start and end dates of the run-in placebo (or the start of double-blind treatment, if applicable; limits included).

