5.6.3 Serious adverse events

An SAE is defined as an AE with “Serious?” = “Yes” on the **Adverse Events** eCRF.

Double-blind treatment-emergent SAEs are all SAEs with onset on or after the double-blind treatment start date [see definition in Section 11.2] up to the double-blind treatment end date [see definition in Section 11.4] plus 30 days (included). Run-in treatment-emergent SAEs are SAEs with onset date between the start and end dates of the run-in placebo (or the start of double-blind treatment, if applicable; limits included).

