13.9 Safety analyses

13.9.1 Adverse events

Output name	Display *	Title (Description)	Analysis set(s)	Key	Mock layout
AEOV	T	Overview of double-blind treatment-emergent adverse events (AEs)	SAF	Yes	LAYAE004
TEAESCPR	T	Double-blind treatment-emergent adverse events (AEs) by primary system organ class (SOC) and preferred term	SAF		LAYAE001
TEAEPR	T	Double-blind treatment-emergent adverse events (AEs) by preferred term	SAF		LAYAE002
TEAERESCP R	T	Double-blind treatment-emergent adverse events (AEs) related to study treatment by primary system organ class (SOC) and preferred term	SAF		LAYAE001
TEAEREPR	T	Double-blind treatment-emergent adverse events (AEs) related to study treatment by preferred term	SAF		LAYAE002
TEAEPRIN	T	Double-blind treatment-emergent adverse events (AEs) by maximum intensity	SAF		LAYAE003
AEOV	T	Overview of run-in treatment-emergent adverse events (AEs)	RIS		LAYAE004
TEAEPR	T	Run-in treatment-emergent adverse events (AEs) by preferred term	RIS		LAYAE002

Output name	Display *	Title (Description)	Analysis set(s)	Key	Mock layout
AE	L	Listing of adverse events (AEs)	RIS		LSTCSR071

* T = Summary Table; L = Listing.
AE = adverse event; RIS = Run-in Set; SAF = Safety Set.

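### Run-in adverse events with a missing onset day can be dated before the first run-in dose and so drop out of the run-in safety tables

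*SAP*

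**What the plan says.** SAP section 12 handles an incomplete AE onset date in two steps. The first applies under a joint condition: "If the end date of the AE is not before the start of double-blind treatment, and if the study treatment start falls in the range" (meaning the dates that the partial entry allows). If it is met, "the study treatment start date is used. In all the other cases the lower limit is used". The same section defines the lower limit: "if the day is missing, the lowest limit is the first day of the given month". The AE onset rule mentions neither run-in start nor informed consent.

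The run-in safety tables use a date window. In SAP 5.6.1.1, "Run-in treatment-emergent AEs are AEs with onset dates between the start and end dates of the run-in placebo" (or double-blind start, if applicable), limits included. SAP 5.6.3 uses the same window: "Run-in treatment-emergent SAEs are SAEs with onset date between the start and end dates of the run-in placebo". The lower edge is fixed in SAP 11.2: "The run-in treatment start date is the first day of intake of study treatment during the run-in period".

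The outputs that use this window, all on the Run-in Set, are the run-in AE overview and "Run-in treatment-emergent adverse events (AEs) by preferred term" (SAP 13.9.1), run-in SAEs by preferred term (13.9.3), and run-in AEs leading to discontinuation by preferred term (13.9.4).

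**The concern.** The first step protects events that reach into double-blind treatment. It gives no comparable protection to an event that began and ended during run-in. If only the month is known and run-in started later in that month, the imputed date precedes the first placebo capsule and the event fails the run-in window. It fails the double-blind window as well, so it appears in no treatment-emergent table.

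The error goes one way, towards undercounting. It affects the period in which previously treated subjects stop their antihypertensive drugs, and Protocol 11.3.5 promises safety summaries for that period. The concomitant-medication start rule, in the same SAP table, does look to the consent date when it is a possible date, so the device was available to the authors.

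**Working it through.** The documents state no figure on this point, so there is nothing to reproduce. The size follows from the rule.

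**Inputs from the SAP**
- Imputed onset: first of the month when the day is missing (section 12).
- Window: from the first run-in dose to the end of run-in, limits included (5.6.1.1, 5.6.3, 11.2).
- Run-in length L: 28 days for treatment-naive subjects, 42 days for subjects on antihypertensive treatment (2.1).

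**Assumptions, not in the documents**
- Run-in start dates are spread evenly over the calendar.
- Onsets are spread evenly over the run-in days.
- Only the day is missing.
- The event resolves before double-blind start.

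**Single subject.** In a month of M days with run-in starting on day s (s ≥ 2), every onset from day s to day M is dated to the 1st and lost. Onsets in later months are dated to the 1st of those months, after run-in start, and are kept. The share lost is min(L, M + 1 − s)/L, and 0 if s = 1. With M = 30:

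| Run-in starts on day | 4-week run-in | 6-week run-in |
|---|---|---|
| 1 | 0% | 0% |
| 2 | 28/28 = 100% | 29/42 = 69% |
| 10 | 21/28 = 75% | 21/42 = 50% |
| 20 | 11/28 = 39% | 11/42 = 26% |
| 30 | 1/28 = 4% | 1/42 = 2% |

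**Average over start days.** Share = Σ(s = 2 to M) min(L, M + 1 − s) / (L × M).
- M = 30, L = 28: (28 + 28 + 27 + … + 1)/(28 × 30) = 434/840 = 51.7%.
- M = 30, L = 42: (29 + 28 + … + 1)/(42 × 30) = 435/1260 = 34.5%.
- M = 31: 462/868 = 53.2% and 465/1302 = 35.7%.

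Enumerating every start date in a 366-day year gives 52.5% and 35.1%. If 25%, 50% or 75% of subjects have the 4-week run-in, the blend is 39%, 44% or 48%.

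**Effect on a whole table.** Let f be the fraction of run-in AEs with a missing onset day. The documents do not give f. If all events resolve before double-blind start, the undercount is about 0.52f (4-week) or 0.35f (6-week). As an illustration only, f = 1% gives 0.5% or 0.35%, and f = 5% gives 2.6% or 1.75%.

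**The undefined term.** The condition names double-blind treatment, but the date substituted is that of study treatment. SAP 11.2 uses the latter term for run-in placebo, and Protocol 10.1.1 starts the treatment-emergent period at study treatment initiation in run-in. For an event that ended before double-blind start the reading makes no difference: the first condition fails and the lower limit applies. For subjects never randomized it does matter. SAP 11.5 sets their double-blind start to missing, so the condition cannot be evaluated as written. If the term means run-in start, the event could be placed there and kept. If it means double-blind start, the event goes to the lower limit.

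**After the fix.** If the run-in start date is used whenever it is a possible onset date, the share dated before run-in start is 0% for both run-in lengths.

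**The case against.** The best case against the point is that it hardly matters. SAP section 12 expects dates to be complete apart from the listed types, AEs are reviewed at every run-in visit, and eCRF entry has programmed checks (Protocol 12.3), so few onset days should be missing. The events are not hidden: SAP 10.9.1 lists all reported AEs, 13.9.1 and 13.9.3 list AEs and SAEs on the Run-in Set, and 13.9.4 lists AEs leading to discontinuation on the Screened Set. Reasons for run-in discontinuation are tabulated separately (13.4.3), without reference to AE onset dates. The affected tables are descriptive, cover placebo only, have a single total column, and none is marked as a key output. All of this stands. It limits the importance of the point but does not make the count right.

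A reader might also infer three stronger things that the documents do not support.
- *That an onset before consent is impossible.* Protocol 10.1.1 counts as an AE a condition detected during the study that may have existed before it, so some true onsets can precede consent.
- *That every day-missing event in a never-randomized subject is lost, with that group put at 1000 − 540 = 460.* The loss depends on the undefined term. The count mixes planning figures: SAP 4.2 lowered the number randomized to 490, and Protocol 3.1 gives about 640 enrolled rather than 1000.
- *That about half of all run-in AEs disappear.* The 52% is a share of day-missing events only, for the shorter run-in, under an even spread.

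**Conclusion.** The point holds as a minor defect. The stated rule gives a wrong count for a definable group: day-missing events that began in the calendar month of run-in start, after the 1st, and resolved before double-blind treatment. Over the whole run-in, that is about 52% (4-week) or 35% (6-week) of day-missing events that resolved before double-blind start. This is an average under even spread; for one subject it runs from 0% to 100% with the start day. The absolute number cannot be derived from the documents and is probably small. Run-in AE, SAE and discontinuation tables are affected; listings, efficacy and dose-response analyses are not. For subjects never randomized, the SAP's wording does not settle the result.

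**What to change.** Make two changes to the AE onset rule in SAP section 12.
1. State that study treatment start in the first sentence means double-blind start.
2. Insert a step before the default: otherwise, if the run-in treatment start date is a possible onset date and the AE did not end before it, use the run-in treatment start date. This applies also to subjects who never started double-blind treatment. Only the remaining cases take the lower limit.

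Do not add an absolute floor at informed consent, because Protocol 10.1.1 admits conditions that predate the study.

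The cost is one or two sentences and about one line of code. The downside is that a few events that began in the screening window of up to 72 h will be counted as run-in events. That errs towards overcounting.
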